**Table 3 - Summary of Adverse Event Reporting Instructions**

EVENT CATEGORY	REPORTING TIMEFRAME	SPECIFIC EVENTS IN THIS CATEGORY	CASE REPORT FORM COMPLETION		
			AE form	Safety complementary form	Other specific forms
Adverse Event	Routine	Any AE that is not SAE or AEPM/AESI Any laboratory, vital sign, or ECG abnormality (non-SAE) other than those specifically listed in another section that is: symptomatic, requiring corrective treatment or consultation, leading to IMP discontinuation or dose modification	Yes	No	No
All Serious Adverse Events	Expedited (within 24 hours of knowledge)	Any AE/AEPM/AESI meeting seriousness criterion per Section 10.4	Yes	Yes	As needed for selected AESI
AESI WITH immediate notification	Expedited (within 24 hours of knowledge)	Clinically significant infections including: Confirmed diagnosis of opportunistic infection based on the investigator's assessment following appropriate diagnostic workups and consultations.  Note: For reporting purposes, any infection from the list of potential opportunistic infections provided in Appendix M should be reported as AESI with immediate notification, even it is not considered to be an opportunistic infection based on the investigator's assessment.  Infection requiring prolonged medication (>14 days). These are infections which require treatment (continuous or intermittent) for > 14 days, with antibiotics, antifungals, or antivirals (exclude when medications are only administered topically). Infections requiring any parenteral antibiotics, parenteral antifungals, or parenteral antiviral agents Tuberculosis or initiation of medication for suspected tuberculosis Parasitic and fungal infections not considered opportunistic infections (Note: for fungal infections only systemic and/or extensive cutaneous cases)	Yes	Yes	Yes
		ALT increase leading to permanent discontinuation	Yes	Yes	Yes
		Grade 4 neutropenia or any neutropenia leading to permanent discontinuation	Yes	Yes	No
		Thrombocytopenia leading to permanent discontinuation	Yes	Yes	No
		Lupus like syndrome	Yes	Yes	No

EVENT CATEGORY	REPORTING TIMEFRAME	SPECIFIC EVENTS IN THIS CATEGORY	CASE REPORT FORM COMPLETION		
			AE form	Safety complementary form	Other specific forms
		Pregnancy of a female patient/or female partner of male patient	Yes	Yes	Yes a
		Symptomatic overdose with IMP/NIMP	Yes	Yes	No
		In addition, AESI WITH immediate notification to always be reported as serious:			
		• Systemic opportunistic infection	Yes	Yes	Yes
		• Grade 4 neutropenia lasting for at least 5 days	Yes	Yes	No
		• Anaphylaxis (defined in Appendix O , report as SAE)	Yes	Yes	No
		• Gastrointestinal perforation	Yes	Yes	Yes
		• Demyelinating events (including suspicion of PML) or significant, unexplained neurological symptoms meeting seriousness criteria	Yes	Yes	Yes
		• Specific cardiovascular events and deaths:	Yes	Yes	No b
		- Myocardial infarction			
		- Stroke			
		- Hospitalization due to unstable angina			
		- Hospitalization due to heart failure			
		- Hospitalization due to transient ischemic attack			
		- Deaths (cardiovascular and noncardiovascular)			
AESI WITHOUT immediate notification (non-SAE)	Routine	Neutropenia grade 3 (<1000 and ≥500 mm  ) without permanent treatment discontinuation	Yes	No	No
		Thrombocytopenia (<100,000/mm  ) without permanent treatment discontinuation	Yes	No	No
		ALT elevation ≥ 3 x ULN without permanent treatment discontinuation	Yes	No	Yes
		Confirmed diverticulitis or gastrointestinal ulceration	Yes	No	Yes
		Demyelinating events or significant, unexplained neurological symptoms not meeting seriousness criteria	Yes	No	Yes
		Asymptomatic overdose with IMP/NIMP	Yes	No	No
• Reminder: Safety Complementary Forms should be completed for all SAEs, AESIs with immediate notification, pregnancies, and symptomatic overdoses					
a This corresponds to "Drug exposure via parent data collection form" used by Global Pharmacovigilance and Epidemiology.					
b No specific form in CRF but a cardiovascular adjudication package needs to be submitted to the Cardiovascular adjudication committee.					

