### **10.2.2 Demyelinating / Neurological events**

Any demyelinating event or significant, unexplained neurological symptom should be considered as an adverse event with prespecified monitoring (see [Section 10.5.4](#)). Refer to [Section 11.2](#) for demyelinating/neurological events requiring permanent treatment discontinuation.

Rarely, biologics have been associated with Progressive Multifocal Leukoencephalopathy (PML). The investigator should check any signs that might be suggestive of a PML at every visit: such as, but not limited to, unusual weakness, loss of coordination, changes in vision, difficulty speaking and sometimes personality changes. In case of suspicion of an event potentially related to a demyelinating event or significant, unexplained neurological symptom during the course of the study, the patient should be referred to a neurologist for a complete examination.

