### **10.5.3 Deleted**

### **10.5.4 Adverse events of special interest/Adverse events with pre-specified monitoring (AESI/AEPM)**

The needs for specific monitoring, documentation, and management of AEPM/AESIs are described in this section.

The decision to report AEPM/AESI as a SAE is the same as for any adverse event; if the event meets any seriousness criteria as per the Investigator's judgment, it should be reported as an SAE. If the AEPM (just as any other adverse event) does not meet seriousness criteria as per the Investigator's judgment, it should be reported as a nonserious event. Certain AEPM/AESI will require immediate notification to the Sponsor, even if not fulfilling seriousness criteria, while others will not.

For the following AEPM/AESI, the Sponsor will be informed immediately (i.e., within 24 hours of knowledge), even if not fulfilling a seriousness criterion, using the corresponding pages in the CRF (to be sent) or screens in the e-CRF, following the same process as described for the SAEs.

- Clinically significant infections including:
  - Confirmed diagnosis of opportunistic infection based on the investigator's assessment following appropriate diagnostic workups and consultations.  
  
Note: For reporting purposes, any infection from the list of potential opportunistic infections provided in [Appendix M](#) should be reported as AESI with immediate notification, even it is not considered to be an opportunistic infection based on the investigator's assessment.
  - Tuberculosis or initiation of medication for suspected tuberculosis
  - Parasitic and fungal infections not considered opportunistic infections (Note: for fungal infections only systemic and/or extensive cutaneous cases)
  - Infection requiring prolonged medication (>14 days). These are infections which require treatment (continuous or intermittent) for > 14 days, with antibiotics, antifungals, or antivirals (exclude when medications are only administered topically).
  - Infections requiring any parenteral antibiotics, parenteral antifungals, or parenteral antiviral agents
- Anaphylaxis (see [Section 10.2.7](#))
- Increased alanine aminotransferase (see [Section 10.2.4](#) and [Appendix L](#)): ALT increase leading to permanent discontinuation
- Neutropenia (see [Section 10.2.5](#) and [Appendix L](#)): Grade 4 or any neutropenia leading to permanent discontinuation
- Thrombocytopenia (see [Section 10.2.6](#) and [Appendix L](#)) leading to permanent discontinuation

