- Lupus like syndrome
- Demyelinating events (including suspicion of PML) or significant unexplained neurological symptoms meeting seriousness criteria
- Gastrointestinal perforation
- Specific cardiovascular events and deaths (see [Section 10.2.10](#)):
  - Myocardial infarction
  - Stroke
  - Hospitalization due to unstable angina
  - Hospitalization due to heart failure
  - Hospitalization due to transient ischemic attack
  - Deaths (cardiovascular and noncardiovascular)

- Pregnancy:
  - Pregnancy occurring in a female patient included in the clinical study (as well as pregnancy occurring in a female partner of a male patient included in the study with IMP/NIMP) will be recorded as a pre-specified AE with immediate notification in all cases. It will be qualified as an SAE only if it fulfills the SAE criteria.
  - In the event of pregnancy in a female patient included in the trial, IMP should be discontinued.
  - The follow-up of the pregnancy in a female participant or in a female partner of a male participant will be mandatory until the outcome has been determined.
- Symptomatic Overdose with IMP/NIMP:
  - An overdose (accidental or intentional) with the IMP is an event suspected by the Investigator or spontaneously notified by the patient and defined as at least twice the dose of IMP during an interval of less than 11 days (NOTE: this definition was less than 6 days for patients on the initial weekly dosing regimen in the study). The circumstances (ie, accidental or intentional) should be clearly specified in the verbatim and symptoms, if any, entered on separate AE forms.
  - An overdose (accidental or intentional) with any NIMP (as defined in [Section 8.2](#)) is an event suspected by the Investigator or spontaneously notified by the patient and defined as at least twice of the intended dose within the intended therapeutic interval. The circumstances (ie, accidental or intentional) should be clearly specified in the verbatim and symptoms, if any, entered on separate adverse event forms.

In addition, the following AESIs/AEPs with immediate reporting must always be considered as medically important if not fulfilling any other seriousness criteria (see [Section 10.4](#)) and reported as serious adverse events.

- Systemic opportunistic infections
- Grade 4 neutropenia lasting for at least 5 days
- Anaphylaxis fulfilling the criteria in [Appendix O](#)

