- Demyelinating events (including suspicion of PML), or significant, unexplained neurological symptoms meeting seriousness criteria
- Gastrointestinal perforation
- Myocardial infarction
- Stroke
- Hospitalization due to unstable angina
- Hospitalization due to heart failure
- Hospitalization due to transient ischemic attack
- Deaths (cardiovascular and noncardiovascular)

For the following AEPM/AESI, the Sponsor **will not** require immediate notification; however if the event meets any seriousness criteria as per the Investigator's judgment, it should be reported as a SAE.

- Neutropenia grade 3 ( $<1000$  and  $\geq 500/\text{mm}^3$ ) without permanent treatment discontinuation (see [Section 10.2.5](#))
- Thrombocytopenia ( $<100\ 000/\text{mm}^3$ ) without permanent treatment discontinuation (see [Section 10.2.6](#))
- ALT elevation  $\geq 3$  x ULN without permanent treatment discontinuation (see [Section 10.2.4](#))
- Confirmed diverticulitis or gastrointestinal ulceration (see [Section 10.2.8](#))
- Significant unexplained neurological symptoms not meeting seriousness criteria (see [Section 10.2.2](#))
- Asymptomatic overdose (definition described above) with IMP/NIMP. The circumstances (ie, accidental or intentional) and the lack of symptoms (ie, asymptomatic) should be clearly specified in the verbatim.

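### Protocol Table 3 lists demyelinating events in a routine, non-serious reporting row that the text of Section 10.5.4 does not provide

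*Protocol*

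**What the plan says.** Protocol Section 10.2.2 brings every such event into scope: "Any demyelinating event or significant, unexplained neurological symptom should be considered as an adverse event with prespecified monitoring". For the reporting route it refers to Section 10.5.4.

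Section 10.5.4 has three relevant lists.

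- **Notice within 24 hours.** The entry is "Demyelinating events (including suspicion of PML) or significant unexplained neurological symptoms meeting seriousness criteria".
- **Always serious.** The listed events "must always be considered as medically important if not fulfilling any other seriousness criteria". The entry is "Demyelinating events (including suspicion of PML), or significant, unexplained neurological symptoms meeting seriousness criteria".
- **No immediate notice.** The only neurological entry is "Significant unexplained neurological symptoms not meeting seriousness criteria".

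Table 3 summarises these instructions. Its block of events always to be reported as serious contains "Demyelinating events (including suspicion of PML) or significant, unexplained neurological symptoms meeting seriousness criteria". Its block of events without immediate notification, labelled non-SAE with a routine timeframe, contains "Demyelinating events or significant, unexplained neurological symptoms not meeting seriousness criteria".

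**The concern.** A summary table is what site staff are likely to have in hand when an event occurs. Here it gives a second, slower route for an event that the text treats as always urgent and always serious. Section 4 of the protocol names demyelinating events among the long-term risks of biologics that motivate this study, and Section 11.2.1 uses demyelinating disease as its example of severe neurologic disease that stops the drug permanently.

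If the routine row were used, the sponsor would get no expedited notice and no safety complementary form. The missing serious flag would carry into the analysis. SAP Section 2.4.4.1 tabulates serious TEAEs by system organ class and preferred term, gives patients with an event per 100 patient-years for serious TEAEs, and shows a serious-TEAE line within each category of special interest. The flag also governs two protocol steps: the sarilumab sample at the onset and end of an SAE (Section 9.3.1) and the assessment for expedited reporting to authorities (Section 10.6).

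**Working it through.** The check compares text with table; the plan has no figure to reproduce.

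**Step 1. Compare the lists without immediate notification.**

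| Item | Section 10.5.4 | Table 3, routine rows |
|---|---|---|
| Grade 3 neutropenia, drug not permanently stopped | listed | same |
| Thrombocytopenia, drug not permanently stopped | listed | same |
| ALT at least 3 x ULN, drug not permanently stopped | listed | same |
| Diverticulitis or gastrointestinal ulceration | listed | same |
| Non-serious unexplained neurological symptoms | listed | listed, with demyelinating events added |
| Asymptomatic overdose | listed | same |

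Five of six items agree. The neurological item is the only one that differs.

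**Step 2. Count the entries for demyelinating events.** Section 10.5.4 has two (24-hour; always serious) and no routine entry. Table 3 has one always-serious entry and one routine entry. Section 10.5.4 has 11 always-serious bullets: systemic opportunistic infection, grade 4 neutropenia of at least 5 days, anaphylaxis, demyelinating or neurological events, gastrointestinal perforation, myocardial infarction, stroke, and hospitalisation for unstable angina, heart failure or transient ischaemic attack, and deaths. Only the neurological bullet has a counterpart among the routine rows of Table 3.

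**Step 3. Compare the two Table 3 rows for one event.**

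| | Always-serious row | Routine row |
|---|---|---|
| Timeframe | within 24 hours | routine |
| AE form | yes | yes |
| Safety complementary form | yes | no |
| Other specific form | yes | yes |
| Forms in total | 3 | 2 |
| Reported as | serious | non-serious |

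**Step 4. Test both readings of the qualifier in the Section 10.5.4 bullets.**

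- *Reading A: the words about meeting seriousness criteria qualify only the neurological symptoms.* Every demyelinating event is then always serious, and the routine row of Table 3 offers a route that the text rules out.
- *Reading B: they qualify both terms.* A non-serious demyelinating event is then possible, but the routine list in Section 10.5.4 omits it.

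Text and table differ on either reading. Two features of the text favour A. The always-serious list exists for events that meet no other seriousness criterion; under B the neurological bullet would only say that serious events are serious. And only under A do the Section 10.5.4 lists cover every demyelinating event, as Section 10.2.2 expects. Neither feature is conclusive, because the Table 3 row is itself evidence for B.

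**Step 5. Trace the analysis.** SAP Section 2.1.3.1 searches all AE forms, including the neurological event form, and SAP Table 1 identifies demyelinating disorders by a narrow standardised MedDRA query. That count does not depend on the reporting route. The serious-TEAE rate in SAP Section 2.5.1 is 100 x n / (sum of exposure times). A patient with no other serious TEAE whose event is not flagged lowers n by 1, and that patient's exposure then runs to the end of the TEAE period instead of stopping at the event. For scale, assuming nearly all enrolled patients are treated, one such patient changes the crude serious-TEAE percentage by 1/111 = 0.9 percentage points in the monotherapy group, and by about 1/(2000 - 111) = 1/1889 = 0.05 percentage points in the combination group.

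**The case against.** The strongest reply is that the protocol, read as a whole, misroutes nothing. Table 3 also carries the always-serious row. Its routine row is limited to events that do not meet seriousness criteria. Under Reading A, being medically important is itself a seriousness criterion (Section 10.4), so no demyelinating event can enter that row and the added words are merely superfluous. Under Reading B the row applies the general rule of Section 10.5.4 for an event of special interest that the investigator does not judge serious, "it should be reported as a nonserious event", and only the text list is incomplete.

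There are other safeguards. Table 3 expedites anything judged serious. Section 10.4 names newly diagnosed or aggravated chronic neurodegenerative disease as medically important, which arguably covers chronic demyelinating disease. Section 10.2.2 requires neurologist referral on suspicion. The routine row still requires the AE form and the event-specific form, and Section 15.4 makes e-CRF data visible to the sponsor on entry.

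Most of this stands, and it keeps the severity low. It does not remove the defect. The always-serious rule is there to take the seriousness decision away from the site for named events; a row for the same event that depends on the site finding it non-serious hands the decision back. A site reading that row alone has no signal that it should be empty.

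A reader might go further and infer that Table 3 sends demyelinating events as a class to routine reporting, or that the demyelination count will be understated. The documents support neither: the same table also lists the event as always serious, and the count comes from the MedDRA search.

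**Conclusion.** The mismatch is real and its severity is low. One row of Table 3 gives demyelinating events a routine, non-serious route that the text of Section 10.5.4 does not give. The exposure is limited to a demyelinating event that a site judges non-serious and files under that row. For such an event the loss is the 24-hour notice, one form and the serious flag. Serious-TEAE counts and rates are affected, the special-interest count is not, and all safety analyses are descriptive. The documents give no demyelinating event rate, so no number of affected events is claimed. The preference for Reading A rests on the structure of the always-serious list and needs the sponsor's confirmation.

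A note on tuberculosis. Section 10.2.1 says that patients at risk for tuberculosis will be permanently discontinued from the study, without defining at risk. A reader might infer a second conflict, in which contacts who are evaluated and cleared must be withdrawn. The documents do not support that strongly: the same section only holds drug until tuberculosis is ruled out, and Section 11.2.1 gives working criteria. It is loose wording that needs a cross-reference.

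**What to change.** 1. In the routine block of Table 3, delete 'Demyelinating events or', so that the row matches the Section 10.5.4 list.
2. Preferably, split the combined bullet in the two Section 10.5.4 lists (24-hour; always serious) and in the always-serious block of Table 3. One bullet would name demyelinating events, including suspected PML, without a qualifier. The other would name significant unexplained neurological symptoms that meet seriousness criteria. The sponsor should first confirm that this was the intent, because under Reading B the split changes the reporting rule.
3. As a note, make the Section 10.2.1 sentence on patients at risk for tuberculosis refer to the criteria of Section 11.2.1, and keep the hold until tuberculosis is ruled out.

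Items 1 and 2 are a few words at four places: one row shortened and three bullets split. They fit the next protocol amendment with a letter to sites and need no new procedures or data. No SAP change is needed.

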## **10.6 OBLIGATIONS OF THE SPONSOR**

During the course of the study, the Sponsor will report in an expedited manner all SAEs that are both unexpected and at least reasonably related to the IMP Suspected Unexpected Serious Adverse Reaction (SUSAR), to the Health Authorities, IECs/IRBs as appropriate and to the Investigators.

In addition, the Sponsor will report in an expedited manner all SAEs that are expected and at least reasonably related to the IMPs to the Authorities, according to local regulations.

In this study, some AEs are considered related to the underlying condition and thus will not be considered unexpected: eg, arthralgia related to RA.

Any other AE not listed as an expected event in the Investigator's Brochure or in this protocol will be considered as unexpected.

The Sponsor will report all safety observations made during the conduct of the trial in the clinical study report (CSR).

## 11 HANDLING OF PATIENT TEMPORARY OR PERMANENT TREATMENT DISCONTINUATION AND OF PATIENT STUDY DISCONTINUATION

The IMP should be continued whenever possible. In case the IMP is stopped, it should be determined if the stop can be made temporarily; permanent IMP discontinuation should be a last resort. Any IMP discontinuation should be fully documented in the CRF. In any case, the patient should remain in the study as long as possible.

### 11.1 TEMPORARY TREATMENT DISCONTINUATION WITH INVESTIGATIONAL PRODUCT(S)

Temporary treatment discontinuation may be considered by the Investigator because of suspected AEs eg, suspected malignancy or because of abnormal laboratory values.

The following is a list of criteria for temporary discontinuation. This list is not exhaustive and IMP may be temporarily discontinued for additional reasons based on Investigator judgment:

- Increase in ALT level  $\geq 3$  x ULN to  $\leq 5$  x ULN and bilirubin  $\leq 2$  x ULN (unless the patient has documented Gilbert's disease). The IMP can be resumed at the dose of 150 mg q2w only after the ALT has returned to a value  $< 3$  ULN and all requirements for resumption of study drug administration are met (see [Section 10.2.4](#) and [Appendix L](#)).
- Decrease in neutrophil count to a level between 500/mm^3 to  $< 1000$ /mm^3 without signs and symptoms of a potential infection. The IMP can be resumed at the dose of 150 mg q2w only after the neutrophils have returned to a value  $\geq 1000$ /mm^3 and all requirements for resumption of study drug administration are met (see [Section 10.2.5](#) and [Appendix L](#)).
- Decrease in platelet count to between 50 000 cells/mm^3 to  $< 100$  000 cells/mm^3 without spontaneous bleeding. The IMP can be resumed at the dose of 150 mg q2w only after the platelet count is  $\geq 100$  000/mm^3 and all requirements for resumption of study drug administration are met (See [Section 10.2.6](#) and [Appendix L](#)).
- Infections requiring oral or parenteral treatment with antibacterial, antiviral and/or antifungal agents (See [Section 10.2.1](#) for additional guidance)
- Surgery requiring temporary treatment discontinuation of biologic DMARD as per applicable guidelines

If the dose is reduced to 150 mg q2w the reduced dose will be maintained for the whole duration of the treatment period.

The IMP can be temporarily discontinued for  $\leq 59$  days (3 IMP doses can be missed).

Reinitiation of treatment with the IMP will be done under close and appropriate clinical/and or laboratory monitoring.

If the restart of the IMP occurs later than 38 days since the last IMP dose (2 IMP doses were already missed), the IMP has to be administered at the study site and the patient to be observed for 30 minutes for any medical events.

NOTE: in case of prolonged decreased neutrophil count to a level between 500/mm^3 to <1000/mm^3 without signs and symptoms of a potential infection and/or prolonged increased ALT level  $\geq 3 \times$  ULN to  $\leq 5 \times$  ULN detailed work-up should be performed before sarilumab is reinitiated to rule out other potential causes of neutropenia or ALT elevation.

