
ASSESSMENT SCHEDULE
	
The last visit (EOT visit) of EFC11072, ACT11575, EFC10832, SFY13370, or EFC13752 will be used as the initial LTS11210 visit. All patients who agree to participate in the LTS11210 will need to sign a new informed consent form specific for this study. At D1, after confirmation of eligibility, patients will be enrolled in the LTS11210 study.
 
Patients will have site visits at weeks 4, 8, and 12, then every 12 weeks until the 2nd year of treatment in the study (Week 96). After 2 years of study participation, safety assessment and laboratory tests will take place at 24-week intervals. In addition, there will be visits at 24-week intervals in between regular study visits for distribution of IMP kits and recording of AEs only (in Portugal and Sweden, hematology and liver function test evaluations will be performed at all IMP dispensing visits until end of treatment). After 264 weeks in LTS11210, some assessments will no longer be required in either scheduled visits or EOT visit (see Section 1.2).
 
Additional laboratory testing (central) including hematology and liver function tests will be performed at week 2, week 6, and week 10 (site or home visits).
 
Efficacy assessments will be performed at Weeks 0, 4, 8, 12 and then every 12 weeks up to Week 96 and then every 24 weeks until the end of treatment.
 
Health economic assessments and Patient Reported outcomes (PROs) defined per initial study will be performed every 12 weeks up to Week 96 and then every 24 weeks until Week 264. PROs will not be assessed after Week 264, including EOT if EOT is after Week 264.
 
Patients who completed EFC11072 Part B will have an additional X-ray evaluation at week 48, 96, 144, 192 (<math>\pm 14</math> days for each evaluation) or at EOT if EOT prior to Week 192.
 
Electrocardiograms (ECGs) will be performed at the initial visit, week 48, 96, 144, 192, 240 and 264 or EOT. ECGs will not be performed after Week 264, including EOT if EOT is after Week 264.
 
Adverse events will be collected throughout the study.
 
Pharmacokinetic samples will be collected at V1 or V1/V2, V4 (Week 4), V7 (Week 12), every 12 weeks thereafter through year 2 and then every 24 weeks until the end of treatment and at the Post-Treatment follow-up visit 6 weeks after the end of treatment.

[figure not shown]

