### **10.2.4 Liver Function**

Transient, generally mild, elevation of transaminases has been observed with sarilumab. See the Clinical Investigator's Brochure (CIB).

Moreover, the co-administration of MTX or NSAID may represent an additional risk factor for observing signs of hepatotoxicity which is reflected in the American College of Rheumatology

(ACR) guidelines (12). The investigator is recommended to monitor transaminases in any patient receiving MTX but without any defined threshold for transaminases to start reducing MTX dosage which is thus left to the investigator judgement.

Please refer to [Section 10.5.4](#) for LFT abnormalities to be reported as AEPM/AESI with or without immediate notification.

The Sponsor relies on the Investigator's judgement for adapting concomitant medication, including dose reduction of MTX dosage, in case of LFT abnormalities within the guidelines below.

In the present protocol, in order to closely follow LFTs, assessment of ALT, AST, alkaline phosphatase, prothrombin time, albumin, total bilirubin, conjugated bilirubin and unconjugated bilirubin will be performed per specifications on the study flow chart (see [Section 1.2](#)).

- The study drug should be permanently discontinued in case of confirmed ALT > 5 ULN or in case of confirmed ALT > 3 ULN and concomitant total bilirubin > 2 ULN (unless the patient has a documented Gilbert's disease). A complete serological and ultrasonography work-up should be conducted in case of ALT > 5 ULN or ALT > 3 ULN and concomitant bilirubin > 2 ULN (see [Appendix L](#)).
- If ALT  $\geq$  3 ULN and  $\leq$  5 ULN and bilirubin  $\leq$  2 ULN, administration of study drug must be temporarily interrupted, and the study Investigator should immediately contact the patient to arrange for repeat LFTs within 48 hours from the Investigator's awareness of the abnormal LFT results:
  - IMP should be temporarily interrupted until the ALT is below < 3 ULN then restarted **at the dose of 150 mg q2w** at the Investigator's discretion.
  - LFTs should be repeated according to the provided guideline and at a minimum of every 7 days until conditions for resumption of IMP administration are met (see [Appendix L](#)).

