Patients will have on treatment visit every 12 weeks starting from Week 24 to Week 96 and then every 24 weeks until EOT. Each visit can be done within  $\pm$  3days.

**12.1.9 Visit 8 (Week 24) to Visit 14 (Week 96) and Visit 16 (Week 120), Visit 18 (Week 144), Visit 20 (Week 168), Visit 22 (Week 192), Visit 24 (Week 216), Visit 26 (Week 240), Visit 28 (Week 264): On treatment visits from Week 24 to Week 264**

This section refers to on-treatment visits with clinical assessments from week 24 up to the end of the initial 264-week period of the study (excluding the IMP dispensing visits).

The Investigator will:

- Check compliance to the study drug and concomitant medication and record any changes in the patient's CRF.

- Record vital signs including body temperature, blood pressure, HR and body weight.
- Physical examination will be done only at weeks: 48, 96, 144, 192, 240 and 264.
- Tuberculosis assessment. In case of suspicion of tuberculosis, refer the patient to a TB specialist for complete examination and additional work-up (see specific instructions in [Section 10.2.1](#)).
- Inquire regarding AE/SAEs.
- Obtain (fasting) blood for complete clinical laboratory determinations including: hematology, clinical chemistry profile, LFTs, lipids profile.
- Save an aliquot of serum (5mL) for storage for future biomarkers at Week 48 (except EFC13752 patients).
- Obtain blood sample for acute phase reactant: hs-CRP.
- Obtain blood sample for rheumatoid factor at week 48, 96, 144, 192, 240 and 264.
- Before dosing obtain sample for serum IL-6 only at week 24, 36 and 48.
- Before dosing, obtain serum sample for PK (sarilumab) and for anti-sarilumab antibody.
- Obtain blood sample for ANA at Week 48, 96, 144, 192, 240 and 264 or sooner if clinically indicated.
- Obtain urine for dipstick urinalysis.
- Obtain urine sample for urine pregnancy test for female of child bearing potential. The patients should be instructed to do the urine pregnancy test at home on a monthly basis during the intervals in between on-treatment clinic visits for the duration of the treatment period. In case of a positive pregnancy test, the patient should be advised to stop the IMP and to contact immediately her study doctor.
- X-Ray of the hands and feet (only for patients who completed EFC11072 Part B (Cohort 2 and Cohort 1 selected dose arms)) at week 48, 96, 144, 192 ( $\pm 14$  days for each evaluation), and transfer images to the central readers.

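### Sections 10.2.4 and 11.1 of the protocol state the temporary ALT hold differently for patients with documented Gilbert's disease

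*Protocol*

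**What the plan says.** Three protocol rules bear on a patient with raised ALT.

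- **Permanent stop (Sections 10.2.4 and 11.2.1).** The drug is stopped for good at ALT >5 x ULN, or at ALT >3 x ULN with "concomitant total bilirubin > 2 ULN (unless the patient has a documented Gilbert's disease" in the 10.2.4 wording. Section 11.2.1 carries an equivalent exception.
- **Temporary hold in Section 10.2.4.** When ALT is ≥3 and ≤5 x ULN and bilirubin is at or below "2 ULN, administration of study drug must be temporarily interrupted". This rule does not mention Gilbert's disease. With it come repeat tests: the investigator is to "contact the patient to arrange for repeat LFTs within 48 hours from the" time of learning of the result, and LFTs are then repeated "at a minimum of every 7 days until conditions for resumption of IMP administration are met". Appendix L is cited.
- **Temporary hold in Section 11.1.** The ALT and bilirubin limits are the same, but a bracket follows the bilirubin limit: "unless the patient has documented Gilbert's disease). The IMP can be resumed at the dose of 150 mg q2w only after the ALT has returned" below 3 x ULN. The section opens by saying that the investigator may consider a temporary stop, and then lists criteria. It gives no retest interval for ALT and refers to Section 10.2.4 and Appendix L.

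**The concern.** A temporary hold for ALT responds to ALT. Gilbert's disease should change only how the bilirubin value is used. Here, whether a Gilbert patient with ALT of 3 to 5 x ULN and bilirubin >2 x ULN is held depends on which section the site consults. Section 10.2.4 is the only one of the two that says the drug must be interrupted, and its bilirubin limit leaves this patient out. Section 11.1 appears to bring the patient back in, but through a bracket that can be read two ways and under a permissive opening.

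What is at stake is consistent handling of a known laboratory effect of sarilumab in a small subgroup. Section 10.2.4 notes that co-administered MTX or an NSAID may add to the liver risk, so the rule should be unambiguous.

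**Working it through.** The plan gives no figure to reproduce. The check treats each rule as a logical condition and compares the outcomes. In x ULN, with A for ALT and B for total bilirubin:

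- Permanent stop: A >5, or (A >3 and B >2 and not Gilbert).
- Hold, 10.2.4: 3 ≤ A ≤ 5 and B ≤2.
- Hold, 11.1, waiver reading (Gilbert lifts the bilirubin limit): 3 ≤ A ≤ 5 and (B ≤2 or Gilbert).
- Hold, 11.1, exemption reading (Gilbert lifts the hold): 3 ≤ A ≤ 5 and B ≤2 and not Gilbert.

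The conditions were evaluated at A = 2.9, 3.0, 4.0, 5.0 and 5.1 and B = 1.0, 2.0 and 2.5, with and without Gilbert's disease. At A = 2.9 no rule acts, and at A = 5.1 the permanent stop always acts. The results at A = 4.0 and 5.0 are identical:

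| Patient | Permanent stop | Hold, 10.2.4 | Hold, 11.1 (waiver) | Hold, 11.1 (exemption) |
|---|---|---|---|---|
| No Gilbert, B ≤2 | no | yes | yes | yes |
| No Gilbert, B >2 | yes | no | no | no |
| Gilbert, B ≤2 | no | yes | yes | **no** |
| Gilbert, B >2 | no | **no** | **yes** | no |

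At exactly A = 3.0 the only change is that the permanent stop does not act in the second row. Both sections still agree there, and that single boundary value is not part of this point.

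1. Without Gilbert's disease, 10.2.4 and 11.1 agree at every value tested.
2. On the waiver reading they differ in the last row: 11.1 holds the drug and 10.2.4 does not.
3. On the exemption reading they differ in the third row: 10.2.4 requires the hold and 11.1 lifts it. In the last row neither section then holds the drug.

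The waiver reading is the better one. The bracket directly follows the bilirubin limit. In the permanent-stop rules the Gilbert bracket attaches to the bilirubin limb alone, since Gilbert patients still stop at ALT >5 x ULN. A waiver in 11.1 also catches exactly the patients whom that exception releases. The note that closes 11.1 points the same way: it asks for work-up before restart after prolonged ALT of 3 to 5 x ULN, with no bilirubin or Gilbert condition. The exemption reading remains a possible mistake, because the near-identical brackets elsewhere do switch off an action.

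**The case against.** The strongest reply is that nothing is missing. On the natural reading 11.1 already holds these patients, so there is no gap in the hold. Other safeguards also apply without a Gilbert exemption. Section 10.2.4 says "A complete serological and ultrasonography work-up should be conducted in case of ALT > 5 ULN or ALT > 3 ULN" with bilirubin >2 x ULN. Section 10.4 lists ALT >3 with bilirubin >2 x ULN among the medically important events, and Section 10.5.4 covers reporting of ALT elevations. Section 10.5.1 requires follow-up until results normalise or stabilise, and 11.1 leaves room for investigator judgment. This stands, and it is why the point is minor. It does not remove the disagreement between two operative sections, one mandatory and one opening permissively.

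A reader might infer two stronger points that the documents do not support.

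- **That the 48-hour and 7-day repeat tests apply only under the 10.2.4 rule.** Among the two section texts they are stated only there, but both sections refer to Appendix L, whose content is not readable in the text available. It may set the retest schedule or settle the meaning of the bracket.
- **That a Gilbert patient could wait for the next scheduled LFT.** The protocol summary says "After 2 years of study participation, safety assessment and laboratory tests will take place at 24-week intervals", and Section 12.1 has 12-week visits before that. Those gaps do not describe a patient held under 11.1. A hold may last at most 59 days, against 12 x 7 = 84 or 24 x 7 = 168 days, and restart needs ALT <3 x ULN, hence a test. For a patient not held, the work-up and follow-up above still apply.

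**Conclusion.** The inconsistency is real and follows from the wording alone. For documented Gilbert patients with ALT of 3 to 5 x ULN, the two sections give different instructions on either reading of the bracket. On the natural reading the difference is confined to bilirubin >2 x ULN, where 11.1 supplies the hold and the mandatory rule in 10.2.4 does not.

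This is a minor patient-safety correction with no effect on the analyses. The documents do not say how many Gilbert patients are among the approximately 2000 planned. The number is assumed to be small, and the conclusion about the wording does not depend on it. Confidence is moderate, because Appendix L could already resolve the matter in practice; the two body sections would still need to agree.

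**What to change.** Use one wording in both sections: *ALT ≥3 to ≤5 x ULN and bilirubin ≤2 x ULN (any bilirubin if documented Gilbert's disease): IMP must be temporarily interrupted, LFTs repeated as in Section 10.2.4, and IMP resumed at 150 mg q2w once ALT is <3 x ULN and all other requirements are met.* This replaces the present bracket in 11.1. In 10.2.4 the existing retest instructions stay under the revised rule. Confirm that Appendix L agrees.

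The cost is one sentence in a protocol amendment, with no new type of assessment. The downside is that a few Gilbert patients may be held, have repeat LFTs while held, and then stay on 150 mg q2w, because 11.1 keeps a reduced dose in place for the rest of treatment. On the natural reading of 11.1 that consequence already applies to them.
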